- Photos (Extra and intra oral).
- Pain questionnaire distributed with explanatory session on it.

➤ **Begin of Retraction:**

- Crimpable hooks added to the arch wire (0.017"x0.025" Stainless steel) distal to the lateral incisor passing near the center of resistance of the anterior segment.
- A ligature wire extending between the second premolar and miniscrews will be used for proper anchorage control.

- Retraction will start on a 0.017"x0.025" Stainless steel wire using elastomeric chain (force applied will be 200 g per side) (24) extending between the crimpable hooks and the molar hooks.
- The force will be measured by a force gauge and reactivated every 4 weeks maintaining constant force of retraction all over the retraction phase.

➤ **Follow up visits**

Patients will be asked to attend for follow up sessions every 4 weeks for:

- Evaluation of miniscrews stability.
- Replacement of the power chain to maintain a force of 200 gm per side for en masse group and 160 gm per side for two step group.
- Impression taking to assesses amount of space closure.
- Recording the pain scoring sheet.

➤ **Criteria for discontinuing or modifying the allocated intervention:**

In cases of prolonged swelling or pain related to the miniscrew, the patient will be given strict oral hygiene measures and may wait for three weeks before the beginning of retraction.

In cases of loose or broken miniscrews, the screw will be removed and replace the miniscrew after total resolution of the inflammation.

In case of non compliant patients.

□ **Post-retraction Questionnaire:**

The patients of both groups will be asked to fill in questionnaires regarding their experience with their allocated technique, during the whole retraction period from day of extraction till the end of retraction.

□ **Retraction records**

Following en-masse and two steps retraction, patients will be referred to the same radiology center to acquire the final cone-beam CT to assess the movement and inclination of anterior teeth.

The final dental model will be used to assess the rate of retraction and molar anchorage loss achieved throughout the study.

□ **Criteria of ending the retraction**

- Class I canine relation
- Normal overjet
- Balanced facial profile
- Closing extraction space

□ **Material Used**

- American Orthodontics Brackets, Roth prescription, 22 slot size.
- American Orthodontics Elastomeric power chains
- American Orthodontics Elastomeric O-ties
- American Orthodontics Ligature wire.

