- Miniscrew, 8 mm length x 1.6mm diameter TAD (Jeil).
- American Orthodontics Arch wires.
- American Orthodontics Molar bands/tubes.

D] Outcomes

[figure not shown]
Primary outcome: is to monitor the Duration of space closure during en-masse and two steps retraction. All outcomes will be assessed as the difference between T0 at the start of retraction and T1 after complete space closure.

Secondary outcomes: is to monitor the changes in the anterior teeth position (final anterior teeth tip, torque and vertical position), anchorage loss, presence of any root resorption and pain associated with the different methods used for retraction.

E] Participant timeline:

1. The principle investigator will screen the potential patients through careful clinical examination of patients at the orthodontic department, Faculty of Oral and Dental Medicine, Future University in Egypt.
2. All recruited patients should fulfil the previously mentioned inclusion and exclusion criteria.
3. Every participant will be asked to sign an informed consent before the beginning of the study.
4. After patient's enrolment, each participant will be asked for pre-intervention records to ensure proper diagnosis.
5. The principle investigator will randomly allocate the patients to one of the intervention groups.

6. Anchorage will be secured by placement of miniscrew, followed by extraction of the first premolar.
7. Active intervention will begin after proper levelling and alignment of the upper arch.
8. The principle investigator will take pre-retraction records for every participant T0.
9. Power chain is used for anterior segment retraction.
10. Each patient will come every 4 weeks for follow up visit, for appliance activation and uptake of impression for interim records + monitoring of recording the VAS sheet.
11. After complete space closure, the principle investigator will take post-retraction records for each participant T1.
12. Every patient will fill up a questionnaire regarding his experience during treatment.
13. The principle investigator will continue the normal treatment and achieve proper finishing for every patient after the end of the study.

F] Sample size calculation:

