Our sample size calculation is based on a previous study comparing the effect of En masse versus two-steps using friction and frictionless mechanics²⁴. Using PS software output, we are planning a study of a continuous response variable from independent Group I and Group II subjects with 1 Group I(s) per Group II subject. In a previous study the response within each subject group was normally distributed with standard deviation 0.76. If the true difference in the Group II and Group I means is 1.0, we will need to study 10 Group II subjects and 10 Group I subjects to be able to reject the null hypothesis that the population means of the Group II and Group I are equal with probability (power) 0.8. The Type I error probability associated with this test of this null hypothesis is 0.05. Considering drop out a sample size 15 per group is appropriate.

G] Recruitment strategy:

The principal investigator will recruit the patients from the clinic of Orthodontic department, Faculty of Oral and Dental Medicine- Future University in Egypt. Screening of patients will continue until the total number of participants for the study is collected.

II) Assignment of interventions:

A] Sequence generation:

The supervisor of the study will apply Computer generated random numbers to randomly assign patients to group A (En-masse) or B (two steps) using Microsoft Office Excel 2007 sheet. The patient numbers will be written in the first column and the supervisor will select function RAND to generate the randomization

number in the second column. These numbers will be sorted according to the randomization number so the first column numbers will be randomly distributed.

B] Allocation concealment mechanism:

The Co-supervisor of the study ([name]) will write the randomization numbers of the patients on opaque white papers folded three times to form sealed envelopes and store it inside a box. The codes for randomization will be securely held at the secretary's office.

C] Implementation:

At the time of intervention, the main operator will send the patient to the secretary's office. Then, the assigned employee will open the box and ask the patient to select one envelope. The main operator will contact the supervisor to know the order and then the main operator will allocate each patient to assign each participant for the corresponding intervention either (En-masse or two steps group) according to the list of codes of randomization.

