C] Harm: The main operator will document and report any harms or unwanted effects during the study intervention to the trial supervisors. Also any unpleasant experience will be reported by the patient in the final questionnaire at the end of the retraction. The main operator will be responsible for the management of any adverse effects or unfavorable side effects resulting from the appliance.

D] Auditing: The supervisor will follow up and review the different interventions and resulting data. And he will periodically follow up the trial progress including recruitment of patients, allocation of participants to study groups; adherence to interventions and reporting of harms. A meeting with the senior supervisor will be set every 3 months to monitor the progress of the study and the need for any adjustments.

V) Ethics and dissemination:

A] Research Ethics Approval:

The Ethical committee in Future University, Egypt will review the protocol before they approve it. The research Ethics committee will evaluate the different interventions of the study to ensure its ethical validity and the potential benefits to the participants.

B] Protocol amendments:

The main investigator will be responsible to complete a formal amendment in case of any modifications or adjustments to protocol that may affect the conduct of the study, as changes in the study design or intervention procedures. The Orthodontics

department, Faculty of Oral and Dental Medicine, Future University in Egypt and the Ethics Committee will approve such amendment before proceeding in the study.

C] Consent:

The main investigator will be in charge for detailed explanation and elaboration of the different steps of the study interventions for each patient. Then will ask every participant to sign a written consent before they begin treatment. The consent will be written in Arabic.

D] Confidentiality:

The main investigator will store any personal information about the participants collected during the study separately from study records in locked files in areas with only access to the supervisors responsible for auditing and analysis. Also, will keep the files in the Department Of Orthodontics, Faculty of Oral and Dental Medicine, Future University and will identify all the reports, data and administrative forms by a coded ID number to maintain participant confidentiality. Participant information won't be used outside the study except with written permission of the participant.

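### Beyond pain scores, patients report harm and experience once, at the end of retraction, with no report required from those who stop early; the operator's harm window is also not consistently defined

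*Combined protocol and SAP*

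**What the plan says.** Section IV) C] Harm sets out two routes for harm data.

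- **Operator:** "The main operator will document and report any harms or unwanted effects during the study intervention to the trial supervisors". No start, end or visit schedule is given.
- **Patient:** "Also any unpleasant experience will be reported by the patient in the final questionnaire at the end of the retraction". Steps 11 and 12 of I) E] Participant timeline confirm the order: post-retraction records are taken after complete space closure, and the questionnaire follows.

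Section I) C] Interventions adds three relevant items. The post-retraction questionnaire asks about experience "during the whole retraction period from day of extraction till the end of retraction". The 4-weekly follow-up visits include "Recording the pain scoring sheet" and a check of miniscrew stability. The criteria for discontinuing or modifying the intervention foresee non-compliant patients, loose or broken screws, and events that may delay retraction: "In cases of prolonged swelling or pain related to the miniscrew". That subsection says how miniscrew problems are managed. It does not say that they are recorded as harms.

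I) F] Sample size calculation allows for losses: "Considering drop out a sample size 15 per group is appropriate". III) C] Statistical Analysis lists an evaluation of patient acceptance, without naming its data source or method. It lists no analysis of harms.

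**The concern.** A report collected only after complete space closure cannot come from a patient who does not get there. The plan expects some such patients, since it enrols more than it needs because of drop-out, but it sets no exit questionnaire or harm form. What patients say about unpleasant experiences other than pain will then describe those who finished. If patients who stop had worse (or better) experiences than those who continue, the result is off in each arm. If stopping differs between arms, so is the comparison, including the one on acceptance.

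Two further features add to this. Completers are asked to look back over the whole time since extraction. The protocol's rationale expects two-step retraction to take longer, so the recall period may be longer in that arm. The operator's route, which could otherwise fill the gap, is tied to a period that the protocol does not define and whose apparent start varies from section to section.

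**Working it through.** **1. The plan's own figure.** Inputs from I) F]: SD 0.76, difference 1.0, power 0.80, alpha 0.05 (two-sided assumed, as sidedness is not stated), 1:1 allocation.

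n per group = 2 × (1.96 + 0.8416)² × 0.76² / 1.0² = 2 × 7.849 × 0.5776 = 9.07, rounded up to 10.

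The exact two-sample t-test calculation gives 10.12, with power 0.795 at 10 per group. The stated 10 reproduces and is not in dispute. It is needed only for the next step.

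**2. The implied drop-out allowance.** No rate is stated. If 15 are enrolled so that 10 remain, 15 × (1 − d) = 10, so d = 5/15 = 33% per arm, or 10 of 30 overall. This is the largest loss that the plan provides for, and so the largest share without a final questionnaire under that allowance.

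**3. What that share can do.** Let p_c be the proportion with a given unpleasant experience among completers, and p_s the proportion among those who stop. The questionnaire estimates p_c. The figure for all randomised patients is (1 − d)p_c + d·p_s. The error is therefore

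p_c − [(1 − d)p_c + d·p_s] = d(p_c − p_s).

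At d = 1/3, the error in an arm is one third of the gap between completers and stoppers. It is zero if there is no gap. In the between-arm comparison it cancels if d and the gap combine to the same product in both arms. The documents give no value for p_c or p_s, so neither the size nor the sign can be computed.

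**4. What remains for a patient who stops early.**

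- Pain scores from the 4-weekly sheets: kept up to the last visit.
- Operator-documented harms: kept, within the operator's window.
- The patient's own report of anything else: not collected.

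**5. When the operator's window opens.** The Harm section's phrase is "document and report any harms or unwanted effects during the study intervention". The protocol supports several starting points.

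- *Timeline, step 7:* "Active intervention will begin after proper levelling and alignment of the upper arch". Miniscrew placement and extraction are step 6, so early miniscrew events would fall before the window.
- *II) C] Implementation:* the word intervention is used for the moment of allocation. Allocation is timeline step 5 and is stated to come before levelling. On this reading miniscrew events are inside.
- *The PICOS statement and I) C]:* the intervention in both arms includes miniscrew anchorage, and screw placement is listed under Interventions. Again they are inside.
- *I) C], clinical procedure:* pre-intervention records are taken right before retraction in the en-masse arm, but after canine retraction in the two-step arm. If the window follows those records, canine-retraction harms would be left out in the two-step arm only.

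The last reading matters most for a comparison, because the window would differ by arm.

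**The case against.** The strongest reply is that harm capture is wider than the Harm section alone suggests. Pain, a central patient-reported harm here, is scored every 4 weeks. The operator is to document any harm, not just harm in completers, and the supervisors review harm reporting. The end questionnaire reaches back to extraction, so for those who finish it covers levelling and alignment. Several sections support a reading of intervention that includes the miniscrews. The listed miniscrew problems lead to delay or replacement, not withdrawal, so nothing shows that those who stop are those who fared badly. No between-arm test of harms is planned.

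Most of this stands, and it rules out several stronger inferences. A reader might conclude that patients report no harm before the end, that early stoppers vanish from the harm data, or that miniscrew events before retraction are excluded. The first two conflict with the pain sheets and the operator's records. The third is possible on one reading but not established. Nor do the documents show that the arms will appear safer than they are, since that depends on who stops and why.

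The reply does not remove the central gap. The visit sheet is described as a pain score. III) A] mentions a questionnaire with items on oral hygiene and discomfort as well, but does not say that these appear on the 4-weekly sheet. The long look-back helps only patients who reach the end. For early stoppers, the remaining source on harms other than pain is an unblinded operator who also manages the adverse effects. Although no harm test is listed, acceptance is to be evaluated for both techniques, and the final questionnaire is its apparent source.

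**Conclusion.** The point holds in limited form. As written, patient reports of harm and experience other than pain come from completers alone. Under the plan's own allowance this could leave out up to 5 of 15 patients (33%) per arm. The resulting error is d(p_c − p_s), at most one third of the completer–stopper gap at that allowance. Whether it is material rests on two things that the documents do not settle: whether stopping is related to experience, and whether it differs by arm. The possibly longer recall in the two-step arm is a secondary weakness whose size cannot be given.

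The operator's window is a matter of undefined and inconsistent wording. It creates a risk of omitting early miniscrew events, or canine-retraction harms in one arm, but does not show that either will be omitted. None of this touches the primary outcome. The change should be made because it is cheap and reports not collected at exit are hard to recover later.

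**What to change.** In IV) C] Harm, with matching edits to I) C] and the participant timeline:

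1. Give the final questionnaire at discontinuation as well as at the end of retraction.
2. Add its unpleasant-experience items to the sheet already completed at each 4-weekly visit, which also shortens recall.
3. State one harm-recording window for both arms, from miniscrew placement to T1 or discontinuation. Say explicitly that it includes levelling and canine retraction, and that miniscrew events are recorded as harms.
4. In III) C], report harms for all randomised patients as the number with at least one event, alongside the time observed in each arm. Name the data source for patient acceptance.

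The cost is a few items on an existing form and one questionnaire at exit. Patients carry slightly more burden, and reported harm rates may be higher because more is asked. No treatment rule changes.
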